Nitrous oxide is an inhaled analgesic that is used in pediatric and adult populations for ambulatory procedures, and is largely viewed as effective and safe. Nitrous oxide also produces a dissociative euphoria and amnesia that could potentially improve patients' anxiety and experience of care during painful or anxiety provoking procedures. We have used patient self-administered nitrous oxide (SANO) in our ambulatory clinic at BIDMC for men undergoing prostate biopsies with good effect and no significant complications. SANO may offer an appealing option for patients who are reluctant to undergo an initial UDS or for those who have not tolerated the study in the past. What we do not know is whether a UDS performed under the influence of SANO will give study results that are accurate and reproduce the bladder function of the patient during their daily routine. In a pediatric population, both ketamine and midazolam have been shown to provide satisfactory sedation without impacting UDS values (Thevaraja, 2012); however, sedation with propofol does negatively impact outcome values (Merguerian, 2006). No studies to date assess whether the administration of SANO will negatively impact UDS results. It is possible that SANO will perform better than ketamine or midazolam, as it is anticipated SANO will reduce anxiety and perception of pain without causing a sedative effect.

We propose a pilot study with 25 patients (14 randomized) to compare the impact of SANO vs Oxygen on UDS parameters of patients undergoing routine UDS. Study procedures will take place in the Clinical Research Center (ST 802, Gryzmish 8). Our primary aim will be to assess whether SANO has any adverse effects on routinely measured UDS variables. We will assess whether

periprocedural SANO negatively impacts operator productivity or increases the difficulty in performing the UDS. A secondary aim will be to assess patient perceived pain and anxiety related to catheter placement and experience of SANO during the UDS.

Specific Aims:

Aim 1: To demonstrate that Self-Administered Nitrous Oxide (SANO) at the time of Urodynamic Study (UDS) does not significantly impact outcome variables during the study.

Hypothesis 1.1: Administration of periprocedural SANO will not impact core UDS outcomes of “Bladder Capacity”, “Maximum Flow Rate”, and “Maximum Detrusor Pressure”

Hypothesis 1.2: Administration of periprocedural SANO will not significantly lengthen the time of the procedure

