As the research pharmacy does not procure nor dispense gaseous inhalants, medical gases used in the study will be managed per protocol and as per BIDMC’s Compressed Gas Cylinder Storage and Handling Policy #: EC-62. Nitrous and oxygen cylinders will be procured through the OR materials management specialist. The tanks for study gases will be stored in an approved gas cylinder storage rack in (Room 385) of the Shapiro Clinic for immediate usage. There is also a gas tank storage area in the Shapiro OR (close to the clinic) for additional storage. Both spaces are secured and locked off hours. Research staff will only access these supplies as necessary for the study.

B. Statistical Considerations

Sample Size Justification

Based on a previous study by Jeon *et al*, the mean (SD) difference in max cystometric capacity (MCC) between repeated UDS fills was 20.6 (11.6) mL. Our sample size calculation to detect this difference between repeated fills (p less than 0.05 significance level) was 14 patients per group ($\alpha=0.05$, power=95%). We will inflate out our sample size to account for any missing data or withdrawals from the study, such that 25 patients may be enrolled. We aim to randomize 14 patients in total.

Data Analysis

All data will be collected and stored securely using the REDCap system. Data will be managed and analyzed by the PI and biostatistical support team at the BIDMC FIRST program. We will also be utilizing the support of outside collaborators, [name] and [name] for data analyses. Collaborators affiliated with outside institutions will not have access to PHI or any identifying information. They will assist with analyses based on de-identified data sent via secure electronic transfer. Upon protocol approval, a data transfer agreement will be initiated to allow for the transfer.

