Primary outcome measures are patient anxiety and pain levels in the N2O group vs the oxygen only group as measured by the VAS and VAS A scores. We are specifically interested in the difference in scores between the two groups. Secondary outcome measures include the difference in several UDS parameters such as Maximum Cystometric Capacity (MCC), Pdet Max, Detrusor Leak Point Pressure (DLPP) Number of Detrusor Contractions, Maximum flow rate (QMax), and Post-void residual. These measurements will be acquired in the standard method of normal UDS. Tertiary outcome measure is operator satisfaction. In each patient group, we will utilize a custom, three question survey following each fill-void cycle to assess any difficulty with catheter placement, patient responsiveness, and patient procedural tolerance with the following options: better than expected, as expected, worse than expected.

We will also be obtaining a pre- and post-procedure State Trait Anxiety Inventory (STAI) and Pain Catastrophizing Scale (PSC) and post-procedure Situational Pain Catastrophizing Scale on all participants and compare the variation in response. Operator ease in performing the UDS will be measured by 3 simple questions assessing patient positioning and ease of catheter insertion.

Lastly, the structured interview will be analyzed according to a predefined qualitative framework to guide how our transcripts will be coded for final data analysis.

C. Subject Selection

Subject Population

The study population will be all patients aged 21 to 85 years referred for UDS within the BIDMC Division of Urologic Surgery. A total of 14 patients will be enrolled for the study.

Eligibility Criteria

Inclusion criteria:

- (1) Scheduled for UDS
- (2) Aged 21 to 85 years
- (3) No learning disabilities
- (4) Suitable for nitrous oxide/oxygen IHS with willingness to undergo two UDS runs during the procedure
- (5) Access to an email and computer

Exclusion criteria:

- (1) Perioral facial hair impeding good mask seal
- (2) Learning disabilities and/or inability to cognitively complete survey questions
- (3) Has any of the following medical conditions:
 - a. Inner ear, bariatric or eye surgery within the last 2 weeks,
 - b. Current emphysematous blebs,
 - c. Severe B-12 deficiency,
 - d. Bleomycin chemotherapy within the past year,
 - e. Heart attack within the past year,
 - f. Stroke within the past year,
 - g. Class III or higher heart failure.

B4. POSSIBLE BENEFITS

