#### Please note:

In our original study protocol, we had based our sample size calculation on a study by Jeon et al. However, as the inter-class correlation was not reported in the study by Joen et al., using their study increases our risk of a type 2 error. In light of this, we performed a literature review of all studies comparing cystometric capacity on repeat cystometry to identify a study that also reports inter-subject correlation. Using the maximum cystometric capacity (MCC) by Broekhuis et al., with an interclass correlation coefficient of 0.86, the sample size calculation to detect clinically relevant a priori difference in 50mL with a power of 82% was 16 patients total. The resulting sample size is less than the amount recruited in our study (19), thus the risk of a type 2 error is less than 20%. The below statistical analysis reflects our updated design.

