### *Outcomes*

An intention-to-treat analysis was performed on 19 participants. MCC was measured as the primary outcome. Secondary outcomes included patient-reported pain and anxiety measured at baseline and immediately before maximum capacity during each UDS run using the Visual Analog Scale for Pain (VAS-P; range 0-10) and the Visual Analog Scale for Anxiety (VAS-A; range 0-10).

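### The protocol's outcome list and the SAP name different primary outcomes (VAS pain and anxiety versus MCC), and the supplied SAP text does not say when or why MCC was designated

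*SAP*

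**What the plan says.** The protocol ranks its outcomes in two incompatible ways.

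- In B1 (Purpose), urodynamics come first: "Our primary aim will be to assess whether SANO has any adverse effects on routinely measured UDS variables". Pain and anxiety come second: "A secondary aim will be to assess patient perceived pain and anxiety related to catheter placement". Hypothesis 1.1, under Aim 1, names bladder capacity, maximum flow rate and maximum detrusor pressure as the core outcomes. Pain and anxiety fall under Aim 2.
- In B3.B, Sample Size Justification, the only calculation uses MCC, on the basis that "the mean (SD) difference in max cystometric capacity (MCC) between repeated UDS fills was 20.6 (11.6) mL".
- In B3.B, Data Analysis, the order is reversed: "Primary outcome measures are patient anxiety and pain levels in the N2O group vs the oxygen only group as measured by the VAS". MCC then appears as one item in the secondary list.

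The SAP's Outcomes section says "MCC was measured as the primary outcome" and lists VAS-P and VAS-A as secondary. Its opening note explains why the source study for the sample size was replaced and ends: "The below statistical analysis reflects our updated design". The protocol cover page carries a similar general notice that the statistical design was updated. Neither notice mentions the primary outcome.

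**The concern.** The primary outcome decides which result is read as the trial's answer. Here the two candidates also call for opposite findings. Aim 1 is met if SANO leaves the urodynamic measures unchanged; Aim 2 is met if SANO improves the VAS scores. A reader holding both documents needs to know which was fixed in advance.

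The only protocol text that ranks outcome measures, as distinct from aims, puts VAS first. The SAP puts MCC first, in text written after recruitment, and gives no reason. Without a dated explanation, the reader cannot judge how far either result may be called confirmatory.

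**Working it through.** **1. The passages side by side.**

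| Place | Pain and anxiety VAS | MCC |
|---|---|---|
| Protocol B1, purpose | Secondary aim | Within the primary aim (UDS variables, none singled out) |
| Protocol B1, Hypothesis 1.1 | Not included (Aim 2) | Bladder capacity, one of three core outcomes |
| Protocol B3.B, Sample Size Justification | No calculation | Sole basis |
| Protocol B3.B, Data Analysis | Primary | Secondary, one of several |
| SAP, Please note | No calculation | Sole basis of the new calculation |
| SAP, Outcomes | Secondary | Primary |

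Three of the four protocol places favour urodynamics and one favours VAS. Of the three, only the sample size singles out MCC.

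**2. The sample-size figures.** These matter here only for the variable they use.

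- Protocol: the standardised difference is 20.6/11.6 = 1.776. At two-sided 0.05 and 95% power, a two-sample t-test needs 10 per group and a paired t-test needs 7 in total. The stated 14 per group is not reproduced.
- SAP: with an intraclass correlation of 0.86, the SD of the paired difference is SD × √(2 × (1 − 0.86)) = 0.529 × SD. Sixteen patients for 50 mL at 82% power requires a paired-difference SD of about 65 mL, that is, a between-patient SD of about 65/0.529 = 123 mL. The supplied text gives no SD, so the figure cannot be checked.

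Both calculations are on MCC. Neither document sizes the trial for VAS.

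**3. Timing of the SAP text.** The note compares the required 16 with the 19 already recruited. The Outcomes section describes the analysis in the past tense. The Statistical Analysis section reports that empty response categories for two operator-rated variables were replaced by 0.5, so at least those data had been tabulated. This dates the text. It does not date the decision to make MCC primary, which could have been taken sooner.

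**4. Disclosure.** The supplied SAP text explains one change, the source of the sample size. Part of the SAP was not available for this review, so the absence of an explanation is established only for the text supplied.

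**5. Error rate if the protocol's outcome list is followed.** That list makes two scores primary, VAS-A and VAS-P. The SAP sets alpha at 0.05 and describes no multiplicity adjustment. If the tests are independent and SANO has no effect on either score:

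1 − (1 − 0.05)² = 1 − 0.9025 = 0.0975, or 9.75%.

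Positive correlation between pain and anxiety would lower this. The figure counts false positives in either direction; in SANO's favour alone it is 1 − (1 − 0.025)² = 4.94%, against 2.5% for a single test. Holm tests the smaller p-value at 0.05/2 = 0.025 and, if that is significant, the larger at 0.05. This holds the overall rate at 0.05.

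**The case against.** The strongest reply is that MCC was the working primary throughout and that the sentence in Data Analysis is the outlier. The study title concerns urodynamic parameters, the primary aim says the same, and the protocol was sized on MCC. The outlying sentence also speaks of two groups, which does not fit a design in which each patient has one run on each gas. On this view the SAP merely settles an internal inconsistency in favour of the stated aim. The VAS scores are not hidden either: they stay as named secondary outcomes with paired estimates and 95% confidence intervals. Holm adjustment may also seem heavy for a pilot.

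Much of this stands. MCC was not introduced after the data, and calling it post hoc by default would misdescribe it. What the reply does not remove is the explicit ranking in the protocol's outcome list, or the fact that Hypothesis 1.1 names three variables rather than one. A protocol that supports two readings makes a dated, reasoned choice more necessary, and the supplied text has none.

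A reader might go further and infer that the primary was switched because of the results. The documents do not support that; they only fail to exclude it. A reader might also count MCC, VAS-P and VAS-A as three chances of a favourable false positive, 1 − 0.95³ = 14.3%. That does not follow, because a significant MCC difference would count against SANO under Aim 1.

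**Conclusion.** The documents contradict each other on the primary outcome, and the protocol contradicts itself. The SAP sides with the protocol's aim and sample size against its outcome list, in text written after recruitment and after some outcome data were tabulated, without saying so in the portion supplied. The consequence is that the prespecified primary cannot be identified from the documents.

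The only error rate that attaches is the 9.75% for two unadjusted VAS primaries, which assumes independence and no true effect on either score. It comes from the protocol naming two primaries, not from the SAP's choice of MCC. It would be tempting to add that a non-significant MCC result occurs 95% of the time when there is no effect, or that alpha has lost its meaning. Neither belongs here: finding no difference when there is none is a correct result, and whether non-significance can support a claim of no impact without an equivalence margin is a separate question.

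**What to change.** 1. Add to the SAP a dated statement that the protocol's Data Analysis section named VAS-A and VAS-P as primary; when MCC was designated primary; why (if so, to match Aim 1 and the sample size); and whether outcome data had been seen by then.
2. Correct the protocol's Data Analysis section so that aim, primary outcome and sample size name the same variable.
3. Report VAS-P and VAS-A in full beside MCC, identified as the outcomes that section named primary, with Holm adjustment across the two.
4. Describe MCC as the variable on which the protocol's sample size was based and which was formally designated primary in the post-recruitment SAP.

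The cost is wording plus one adjustment on existing data. The primary claim then carries a disclosed caveat, and the VAS claims face a slightly stricter threshold.

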### *Statistical Analysis*

Bivariate analyses were performed to compare UDS outcomes, pain and anxiety scores, and operator-reported outcomes during SANO and Oxygen runs. Paired Wilcoxon signed rank sum test and McNemar's chi-squared Tests were used for continuous and categorical variables, respectively. For two variables (Patient Responsiveness during UDS and Observed Patient Procedure Tolerance), there were no categorical responses for the treatment arms. Therefore, the substitution of zero with a value of 0.5 was used to satisfy the chi-squared conditions. Subgroup analysis was performed to compare key UDS outcomes between treatments for patients randomized to either Oxygen or SANO on the 1st run. Additionally, a sensitivity analysis was performed comparing UDS outcomes between treatment groups for the 1st UDS run only. An alpha of 0.05 and 95% confidence intervals (CI) were used as criteria for statistical significance. For continuous data, a pairwise version of the Hodges-Lehman Median Difference method was used to estimate a pseudo-median difference and corresponding 95% CI. Data were collected and stored using REDCap electronic data capture tools hosted at Beth Israel Deaconess Medical Center. Analyses were performed using Microsoft Excel (v16.66.1), R (v4.3.0), and SPSS (v29.0).

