Hypothesis 1.3: Administration of periprocedural SANO will allow the operating APP to perform the procedure with the same ease as on those patients who do not have SANO.

Aim 2: To assess effectiveness of SANO in decreasing patient perceived anxiety and pain related to UDS.

Hypothesis 2.1: Administration of periprocedural SANO will improve patients’ experience during the UDS as measured by VAS (visual analogue scale) score.

Hypothesis 2.2: Administration of periprocedural SANO will result in minimal side effects for the patients and will allow the patient to drive home independently.

B2. SIGNIFICANCE AND BACKGROUND FOR THE STUDY**Burden of Urodynamic Study**

Urodynamic testing is an ambulatory procedure that is considered the gold standard for evaluating lower urinary tract symptoms (LUTS) in both female and male patients. Though not required for all patients with LUTS, a UDS can be particularly helpful in evaluating those patients who do not respond to first line treatment algorithms for LUTS. There are certain patient populations, such as children and adults with spina bifida, who require routine UDS evaluations to assess for worrisome changes that may result in damage to their urinary system. Many of these patients can develop an increasing reluctance to undergo UDS due to poor memories of prior experience. Studies have shown that up to 26% of patients are unwilling to undergo a future UDS (Yokoyama, 2005). In part, this dissatisfaction is due to the innate discomfort of the procedure; however, embarrassment and shame during UDS has also been found, especially in women (Yeung, 2014). Children may particularly bear a significant burden during UDS, with studies showing “serious” or “severe” distress in 61% of children undergoing UDS (Herd, 2006).

Nitrous Oxide as an adjunct for Procedural Pain

Inhaled nitrous oxide is commonly used for patient analgesia and anxiolysis outside of the US, and is gaining traction in the US. For example, use of nitrous oxide during labor occurs in 43% of Canadian deliveries and 62% of deliveries in the UK (Rooks, 2007). This has led to recent adoption and promulgation of nitrous oxide by AWHONN (Association of Women's Health Obstetric and Neonatal Nurses) as a "vital component in the provision of quality of maternity care" (Practice Brief, 2018). Nitrous oxide has also been adopted in US pediatric clinical settings, including Boston Childrens Hospital's Emergency Department.

Administration:

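### Replacing zero counts by 0.5 does not validate McNemar's chi-squared in 19 pairs; for two tertiary operator items it may hide a difference if three rating levels were kept

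*SAP*

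**What the plan says.** The SAP (Outcomes) gives the sample: "An intention-to-treat analysis was performed on 19 participants". Each participant contributes a SANO run and an oxygen run, so the operator ratings are paired.

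The SAP (Statistical Analysis) assigns the tests: "Paired Wilcoxon signed rank sum test and McNemar's chi-squared Tests were used for continuous and categorical variables, respectively". It then makes an exception: "For two variables (Patient Responsiveness during UDS and Observed Patient Procedure Tolerance), there were no categorical responses for the treatment arms". For these two items, "the substitution of zero with a value of 0.5 was used to satisfy the chi-squared conditions". The decision rule is "An alpha of 0.05 and 95% confidence intervals (CI) were used as criteria for statistical significance". The SAP names no exact test and no analysis without the substitution. It does not state the dimension of the tables, which cells were zero, or whether a continuity correction was applied.

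The protocol (B3.B, Data Analysis) ranks the outcome: "Tertiary outcome measure is operator satisfaction". It describes a three-question survey after each fill-void cycle covering catheter placement, responsiveness and tolerance, "with the following options: better than expected, as expected, worse than expected". Hypothesis 1.3 (protocol B1) expects that SANO will let the operator "perform the procedure with the same ease as on those patients who do not have SANO".

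**The concern.** McNemar's chi-squared relies on a large-sample approximation to the distribution of the discordant counts. When those counts are few, adding 0.5 to empty cells changes the statistic but does not supply the missing information. An exact binomial test on the discordant pairs needs no filler.

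The direction of the distortion also matters. When changes run one way, the fill pulls the statistic towards no difference, which is the result Hypothesis 1.3 predicts. Protocol B1 stresses that urodynamic testing depends on continuous verbal feedback from the patient. Responsiveness is therefore a natural place for an unwanted effect of nitrous oxide to appear, and it is one of the two affected items.

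**Working it through.** **Inputs.** From the SAP: 19 pairs, alpha 0.05, McNemar's chi-squared, zeros replaced by 0.5. From the protocol: three rating levels. Neither document gives an observed table, discordant count or power for these items, so there is no stated figure to reproduce. All discordant counts below are assumptions, shown over a range. The notation b:0 means b patients changed in one direction and none in the other.

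**Formulas.**
- Exact two-sided sign (binomial McNemar) test for b:0: p = 2 × 0.5^b.
- Two levels, 1 df: (b − c)²/(b + c). With the fill at c = 0 this is (b − 0.5)²/(b + 0.5). With continuity correction it is (b − 1.5)²/(b + 0.5).
- Three levels (Bowker's extension of McNemar): the sum of (b − c)²/(b + c) over the three off-diagonal pairs, on 3 df.

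**What the fill does on three levels.** Without it, a (b, 0) pair contributes b²/b = b. With it, the pair contributes (b − 0.5)²/(b + 0.5), which is below b. An empty pair becomes (0.5, 0.5) and adds nothing, but its degree of freedom is still counted.

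**Three levels kept, all changes in one pair of categories.**

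| Split | Exact p | 3 df, no fill | 3 df, 0.5 fill |
|---|---|---|---|
| 6:0 | 0.031 | 0.112 | 0.199 |
| 7:0 | 0.016 | 0.072 | 0.131 |
| 8:0 | 0.008 | 0.046 | 0.085 |
| 9:0 | 0.004 | 0.029 | 0.055 |
| 10:0 | 0.002 | 0.019 | 0.035 |

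For 8:0, the exact p is 2 × 0.5^8 = 0.0078. The unfilled statistic is 8 and the filled one is 7.5²/8.5 = 6.62. The fill alone reverses the decision at 8:0 and 9:0. At 6:0 and 7:0 the 3-df test has already lost significance without it.

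**Three levels kept, changes spread over the pairs.** With 4, 4 and 3 changes, all in one direction, the filled statistic is 2 × 3.5²/4.5 + 2.5²/3.5 = 5.44 + 1.79 = 7.23, giving p = 0.065. The unfilled statistic is 11 (p = 0.012), and the exact test gives 2 × 0.5^11 = 0.001. Here 11 of 19 patients move the same way, none the other, and the filled test does not reject.

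**Collapsed to two levels.**

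| Split | Exact p | No fill | 0.5 fill | 0.5 fill, continuity-corrected |
|---|---|---|---|---|
| 4:0 | 0.125 | 0.046 | 0.099 | 0.239 |
| 5:0 | 0.0625 | 0.025 | 0.055 | 0.136 |
| 6:0 | 0.031 | 0.014 | 0.031 | 0.078 |
| 7:0 | 0.016 | 0.008 | 0.018 | 0.045 |
| 8:0 | 0.008 | 0.005 | 0.010 | 0.026 |

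The uncorrected filled test agrees with the exact test at 0.05 in every row. With continuity correction, only 6:0 is lost.

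**Power in one assumed scenario.** Take 19 pairs, ratings of better/as/worse at 10/80/10% on oxygen and 0/50/50% on SANO, independent within patient. Simulated power is about 75% for the exact sign test, 46% for the 3-df test without the fill and 19% with it. Repeat runs differ by about one percentage point. Of the 56-point loss (75 − 19), 29 points (75 − 46) come from the unordered 3-df test and 27 (46 − 19) from the fill. If the same ratings are collapsed to worse/not worse, the filled uncorrected test has about 75% power and exact McNemar about 66%.

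**The case against.** The strongest reply is that the SAP never describes a three-level test. It names McNemar's test, which in its classical form is for a 2×2 table, and mentions neither 3 df nor a multi-category extension. The three options appear only in the protocol's statistical section, which the cover page says has been updated. That section also describes the operator questions a second way, as covering positioning and catheter insertion. On a 2×2 table the fill does little harm. At 4:0 and 5:0 it even moves the unfilled p-values (0.046 and 0.025) back to the non-significant side, where the exact test lies.

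This stands as a limit on size. It does not rescue the method, because the agreement on a 2×2 table does not come from the chi-squared conditions having been met. The protocol does specify three levels and no collapsing is described. The SAP's remark about absent categorical responses would fit an unused category, for which 0/0 leaves the three-level statistic undefined. That is an inference, and the ambiguity itself needs correcting.

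Three stronger readings are tempting, and the documents support none of them:
- **Data were invented.** The SAP discloses a pseudo-count used in a test. No patient's rating is altered.
- **A real operator-reported difference was concealed.** No observed counts are given. The documents show only that a difference could be hidden under one reading.
- **The SAP's method has 19% power.** That figure belongs to one reading of the table and one assumed scenario, and about half of the loss is due to the unordered 3-df test.

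**Conclusion.** The substitution is wrong as a justification for the chi-squared test: 0.5 in empty cells does not validate a large-sample approximation in 19 pairs, and an exact test was available. The consequence is conditional. If the three levels were kept, the filled test is strongly conservative in the direction that favours Hypothesis 1.3 and can miss 8:0, 9:0 or an 11:0 spread. If the ratings were collapsed to two levels, the effect is small, and at most the 6:0 split is lost through a continuity correction.

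The point concerns two tertiary items in a pilot. Maximum cystometric capacity and the pain and anxiety scales are continuous measures under the SAP's Wilcoxon rule and are unaffected. Severity is minor to moderate; a reader might treat it as something that must be fixed before any result can be used, but its reach does not support that.

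An exact test would not by itself establish equal ease. At 5:0 the exact p is 0.0625, which is non-significant. Yet the 95% exact interval for the share of changes going against SANO would run from 0.025^(1/5) = 0.48 up to 1.

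**What to change.** In SAP, Statistical Analysis:

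1. Delete the 0.5 substitution.
2. State whether each operator item was analysed at two or three levels, and clarify what was absent in the two items named.
3. Show the raw paired table (SANO by oxygen) for each operator item.
4. Code ordered three-level ratings −1/0/+1 and use an exact sign test or exact signed-rank test. For two-level items use the exact binomial McNemar test.
5. Give an exact confidence interval for the paired difference.
6. State that a non-significant result will not be read as proof of the sameness in Hypothesis 1.3.

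The cost is a few sentences in the SAP, a re-run of two comparisons on data already collected, and small tables of 19 pairs. No new data are needed.

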Confirmation of a patient's eligibility and completed informed consent will be documented in REDCap before proceeding with study procedures. Then, patients will complete the Brief Pain Inventory (see attached) via REDCap questionnaire that is sent to the patient's email. The BPI is a well-validated measure that assesses intensity of current pain and interference of pain in the patient's life (Dworkin, 2005). If the patient does not complete the BPI electronically before the day of procedure, they will be offered the opportunity to complete it on the day of their procedure prior to the UDS.

Randomization

A UDS is comprised of two phases: a filling phase and a voiding phase. For the purposes of our study, subjects will undergo two “runs”, one with SANO and one with Oxygen.

Subjects will be randomized to either:

- Group 1: First run with SANO, second run with Oxygen
- Group 2: First run with Oxygen, second run with SANO

The results of the randomization will not be disclosed to patients as part of the study (patient-blinded), or to the operator of the UDS (provider-blinded). The randomization module in REDCap will be used to randomize subjects between the two groups.

The catheters will be placed before the first run, and left in place through the second run (that is, the catheters will not be changed between the two runs). All subjects will receive SANO during catheter placement. The UDS will be performed by a BIDMC advanced care practitioner according to usual clinical practice. It is standard-of-care for patients to undergo two complete UDS runs:

- First run: Filling phase, voiding phase (~8 minutes)
- Second run: Filling phase, voiding phase (~8 minutes)

Therefore, we do not believe the utilization of two runs to be a significant increase in burden on the patient.

Pre-procedure Evaluation

On the day of the UDS, the patient will be brought to the exam room where pre-procedure vitals are obtained. The six-item State Trait Anxiety Inventory and the six-item Pain Catastrophizing Scale will be administered to assess patient’s baseline pain and anxiety levels. Information of inhaled gas administration and how to self-administer will be explained to the patient using templated verbal instructions. It will be emphasized that if at any point during the procedure, the patient feels uncomfortable with the inhaled gas, the team will help remove the mask.

Periprocedural Intervention

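### The crossover's gas comparison is not adjusted for run order, and the by-sequence tests cannot separate gas from run order

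*SAP*

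**What the plan says.** The protocol (B3.A, Randomization) sets up a two-sequence, two-run crossover: "Group 1: First run with SANO, second run with Oxygen" and "Group 2: First run with Oxygen, second run with SANO". On allocation it says only that "The randomization module in REDCap will be used to randomize subjects between the two groups"; it gives no ratio, no blocking and no achieved split.

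The SAP makes maximum cystometric capacity (MCC) the primary outcome and analyses 19 participants. Under Statistical Analysis, continuous outcomes in SANO runs and oxygen runs are compared by "Paired Wilcoxon signed rank sum test", with a paired Hodges-Lehmann estimate and 95% CI. No run or sequence term appears, and no run-order estimate is planned. The same paragraph then gives an analysis by sequence: "Subgroup analysis was performed to compare key UDS outcomes between treatments for patients randomized to either Oxygen or SANO on the" first run. It also includes a sensitivity analysis that compares the gases on first-run data alone.

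The protocol's sample size section reports from a cited study that "the mean (SD) difference in max cystometric capacity (MCC) between repeated UDS fills was 20.6 (11.6) mL". The SAP later drops that study for sample sizing, because it did not report a correlation between fills.

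**The concern.** Run order is built into this design, and the protocol's own cited source suggests that a repeat fill may not give the same MCC as the first. A paired analysis that pools the sequences leaves any run-order effect in the differences. There it adds spread and, if the sequences are unequal in size, a bias. Nineteen patients cannot split equally.

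The by-sequence tests are the more serious problem. In SANO-first patients, SANO minus oxygen is also run 1 minus run 2; in oxygen-first patients it is also run 2 minus run 1. A difference in either subgroup may come from the gas, from repeat filling, or from both. The SAP sets alpha at 0.05 and gives no warning about this. Repeat filling alone could therefore appear as two SANO effects in opposite directions, or could mask a real effect in one subgroup. The trial's first aim is to show that SANO does not disturb UDS measurements, so either error bears on its main message.

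**Working it through.** **Inputs from the documents.** N = 19; clinically relevant difference 50 mL; ICC 0.86; power 82% at 16 patients (all SAP). Between-fill difference 20.6 mL, SD 11.6 mL (protocol).

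**Assumptions.** Two-sided alpha 0.05, normal differences, no carryover. The split is unknown: 10/9 is taken as the base, with 12/7 as an uneven case. P = 20.6 mL is illustrative.

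**The SAP's own figure.** The 16 patients cannot be reproduced, because no SD is given. Solving a paired t-test for 82% power at 50 mL and n = 16 gives an SD of the paired difference of about 65 mL (about 70 mL by normal approximation). Since SD of difference = single-run SD × √(2(1−0.86)) = single-run SD × 0.529, the single-run SD is about 65/0.529 = 123 mL.

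**What each analysis estimates.** Let T be the gas effect (SANO minus oxygen) and P the run effect (run 2 minus run 1), with n1 patients SANO-first and n2 oxygen-first.
- SANO-first: SANO minus oxygen is centred on T−P.
- Oxygen-first: SANO minus oxygen is centred on T+P.
- Pooled: T + P(n2−n1)/19, and P² is added to the variance of the differences (almost exactly, at near-equal splits).
- Run-adjusted: run 2 minus run 1 is centred on P−T in SANO-first and P+T in oxygen-first patients. Half the gap between sequences is T, and the midpoint is P.

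**By-sequence tests, T = 0, P = 20.6.** The subgroups are centred on −20.6 and +20.6 mL, a gap of 41.2 mL. Simulated signed-rank rejection rates at SD 65 mL and 10/9 are about 14% (n = 10) and 11% (n = 9), against a nominal 5%.

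**Pooled analysis, bias.** 20.6 × 1/19 = 1.1 mL at 10/9; 20.6 × 5/19 = 5.4 mL at 12/7. Under simple randomisation, a split of 12/7 or more uneven, in either direction, has probability 36%.

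**Pooled analysis, precision at 10/9, SD 65.**
- Pooled SD = √(65² + 20.6²) = 68.2; CI half-width = 2.101 × 68.2/√19 = 32.9 mL.
- Run-adjusted half-width = 2.110 × (65/2) × √(1/10 + 1/9) = 31.5 mL.

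**Power for +50 mL, SD 65, P = +20.6 (simulated).**

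| SANO-first / oxygen-first | Pooled signed-rank | Run-adjusted rank-sum |
|---|---|---|
| 10/9 | 83% | 85% |
| 9/10 | 86–87% | 85% |
| 12/7 | 76% | 83% |
| 7/12 | about 92% | about 83% |

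The pooled test gains or loses according to whether the bias happens to point with or against the effect.

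**First-run-only comparison, 10 v 9, single-run SD 123.** Half-width = 2.110 × 122.8 × √(1/10 + 1/9) = 119 mL; power for 50 mL is about 13%.

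**If the within-patient SD is small relative to P.** At the protocol's SD of 11.6 mL and a 10/9 split, the pooled half-width is 11.4 mL against 5.6 mL adjusted. With no gas effect the pooled test rejects almost never (adjusted: about 4%), and each subgroup test rejects about 99% of the time.

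**The case against.** The strongest reply is that the primary comparison is sound. Order is randomised, so the bias averages to zero over allocations. At 10/9 it is 1.1 mL, about 2% of the 50 mL difference, and under simple randomisation the pooled test keeps its type I error at about 5%. On average over splits, adjustment gains almost no power at SD 65 mL. All of this stands: a reader might infer that the primary test is invalid, and the documents do not support that.

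Nor does the plan ignore run order altogether. The first-run-only analysis is free of it. But that analysis gives up the pairing, and with an interval of about ±119 mL it cannot resolve a 50 mL question.

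The 20.6 mL is a weak anchor. The protocol gives no direction, and the figure may be an absolute difference rather than a signed shift. A reader might take it as an established run-order effect, or take the near-certain false positives at SD 11.6 mL as this trial's error rate. Neither follows. That SD comes from the study the SAP set aside for sample sizing, and it is less than a fifth of the SD that the SAP's current calculation implies.

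Finally, shown side by side, the two sequence results do carry information: their mean is T and half their difference is P. That is a reason to keep them as description. It does not make either one a test of SANO.

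**Conclusion.** The point holds in a limited form. The confounding of gas with run order in the by-sequence tests is a matter of algebra and holds for any nonzero P of either sign, at any split. Its size does depend on assumptions: about 11–14% false positives per subgroup if P is 20.6 mL, the SD of differences is about 65 mL and the split is 10/9.

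For the pooled primary analysis the missing adjustment is a modest inefficiency. It brings a small bias whose direction depends on the sign of P and on the split, and both are unreported. It matters more if the split is uneven or if the within-patient SD is small relative to P. Because a better analysis of the same data is nearly free, the change is worth making.

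**What to change.** - Estimate the gas effect with a run-adjusted crossover analysis: compute run 2 minus run 1 for each patient, compare the two randomised sequences by the exact Wilcoxon rank-sum test, and report half the Hodges-Lehmann shift (oxygen-first minus SANO-first) with half its CI limits.
- A mixed model with gas, run and patient is an alternative, not an equivalent. It relies on normality and, where a patient has one usable run, draws on between-patient information.
- The SAP is written in the past tense, so report the adjusted result beside the pooled one and identify it as a later change.
- State the number randomised to each sequence and the estimated run-order effect with its CI.
- Present the within-sequence results as descriptive only, without p-values offered as tests of SANO.

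The cost is about one degree of freedom, a few lines of R and a short SAP revision. No new data are needed.
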